7.2. Screening and Critical Baseline Assessments

Cardiovascular medical history and risk factors (as detailed in the eCRF) will be assessed at screening.

Entry into the study requires a stable Hgb of 9.0 - 11.5 g/dL. A stable Hgb value will be confirmed from three Hgb values taken during the screening period at Day -28, Day -14 and Day 1 (randomization) as outlined in Section 5.1.

7.3. Efficacy

Hgb values to be used in the determination of the primary endpoint (Hgb change from baseline at Day 29) will be measured by the central laboratory as part of the Clinical Safety Laboratory Assessments (Section 7.4.6). Day 1 measurement will serve as the baseline value.

7.4. Safety

Regular monitoring of hematology, blood chemistry and vital signs will occur throughout the study. Serum pregnancy tests will be performed in women of child-bearing potential at Screening and Follow-up.

7.4.1. Adverse Events (AE) and Serious Adverse Events (SAEs)

The definitions of an AE or SAE can be found in Section 12.5.

The investigator or their designees are responsible for detecting, documenting and reporting events that meet the definition of an AE or SAE.

7.4.1.1. Time period and Frequency for collecting AE and SAE information

- Any SAEs assessed as related to study participation (e.g., protocol-mandated procedures, invasive tests, or change in existing therapy) or related to a GSK product will be recorded from the time a subject consents to participate in the study up to and including any follow-up contact.
- AEs will be collected from the start of Study Treatment (Day 1) until the Follow-up visit (see Section 7.4.1.4).
- Medical occurrences that begin prior to the start of study treatment but after obtaining informed consent may be recorded on the Medical History/Current Medical Conditions section of the eCRF.
- All SAEs will be recorded and reported to PPD within 24 hours, as indicated in Section 12.5.4.
- Investigators are not obligated to actively seek AEs or SAEs in former study subjects. However, if the investigator learns of any SAE, including a death, at any time after a subject has been discharged from the study, and he/she considers the event reasonably related to the study treatment or study participation, the investigator must promptly notify PPD.

NOTE: The method of recording, evaluating and assessing causality of AEs and SAEs plus procedures for completing and transmitting SAE reports to PPD are provided in Section 12.5.6.

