12.5.4. Recording of AEs and SAEs

AEs and SAE Recording:

- When an AE/SAE occurs, it is the responsibility of the investigator to review all
 documentation (e.g., hospital progress notes, laboratory, and diagnostics reports)
 relative to the event.
- The investigator will then record all relevant information regarding an AE/SAE in the eCRF
- It is **not** acceptable for the investigator to send photocopies of the subject's medical records to GSK in lieu of completion of the GSK, AE/SAE eCRF page.
- There may be instances when copies of medical records for certain cases are requested by GSK. In this instance, all subject identifiers, with the exception of the subject number, will be blinded on the copies of the medical records prior to submission of to GSK.
- The investigator will attempt to establish a diagnosis of the event based on signs, symptoms, and/or other clinical information. In such cases, the diagnosis will be documented as the AE/SAE and not the individual signs/symptoms.

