12.5.6. Reporting of SAEs to GSK

SAE reporting to GSK via electronic data collection tool

• Primary mechanism for reporting SAEs to GSK will be the electronic data collection tool.

CONFIDENTIAL

- If the electronic system is unavailable for greater than 24 hours, the site will use the paper SAE data collection tool and fax it to the PPD Safety Hotline.
- Site will enter the serious adverse event data into the electronic system as soon as it becomes available.
- After the study is completed at a given site, the electronic data collection tool (e.g., InForm system) will be taken off-line to prevent the entry of new data or changes to existing data.
- If a site receives a report of a new SAE from a study subject or receives updated data on a previously reported SAE after the electronic data collection tool has been taken off-line, the site can report this information on a paper SAE form and fax it to the PPD Safety Hotline or to the Medical Monitor by telephone.
- Contacts for SAE receipt can be found at the beginning of this protocol on the Medical Monitor/Sponsor Information Page.

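### The paper-and-fax backup for SAE reports is triggered by an outage of more than 24 hours, which is longer than the whole 24-hour reporting window, so a site that follows it can report late

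*Protocol*

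**What the plan says.** Protocol Section 7.4.1.1 states the deadline: "All SAEs will be recorded and reported to PPD within 24 hours, as indicated in Section 12.5.4". It does not say when the 24 hours begin. A NOTE at the end of that section sends the reader to Section 12.5.6 for how SAE reports are completed and transmitted.

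Section 12.5.6 describes the routes:

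- Normal route: "Primary mechanism for reporting SAEs to GSK will be the electronic data collection tool".
- Backup during an outage: "If the electronic system is unavailable for greater than 24 hours, the site will use the paper SAE data collection tool and fax it". The recipient is the safety hotline.
- When the system returns: "Site will enter the serious adverse event data into the electronic system as soon as it becomes available". No separate time limit is attached.
- After the study has finished at a site: a new or updated report that arrives "after the electronic data collection tool has been taken off-line, the site can report this information on a paper SAE form" and faxed, or made to the Medical Monitor by telephone.

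Section 12.5.4, which the deadline sentence cites, deals with recording: "The investigator will then record all relevant information regarding an AE/SAE in the eCRF". It contains neither a time limit nor an outage procedure.

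**The concern.** A backup route exists so that the deadline can be met when the normal route fails. Here the stated trigger for the backup exceeds the deadline itself. A site that treats Section 12.5.6 as its outage procedure could wait beyond the limit in Section 7.4.1.1 and still believe it had followed the protocol.

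What is at stake is the timing of safety information, not an estimate. Section 4.6.2 relies on an internal safety review team that monitors accruing data blinded. In the risk table of Section 12.3 that monitoring is listed against every clinical risk, and it is the only mitigation listed for pulmonary artery hypertension, cardiomyopathy and exacerbation of rheumatoid arthritis. The SAP (Section 8.2.2.1 and the note to Table 3.18) has the same team identify adverse events of special interest while the study runs. The sponsor's duty to inform regulators (Section 7.4.1.6) also depends on the site's report. With a treatment period of 29 days, a lost day is not negligible.

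**Working it through.** The plan gives no figure to reproduce here. The check sets the two time limits on one clock.

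**Inputs**

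- Deadline: 24 hours (Section 7.4.1.1).
- Backup trigger: more than 24 hours of unavailability (Section 12.5.6).
- Start of the clock: not stated. I take the site learning of the event as hour 0. This is an assumption.

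**Formula.** Let the outage be counted from hour s, with s negative if it began before the site learned of the event. Then:

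- the paper route is triggered just after hour s + 24;
- the deadline is hour 24;
- time left on paper is just under 24 − (s + 24) = −s hours, so there is none when s is 0 or more.

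| Outage counted from | Paper triggered just after | Time left before hour 24 |
|---|---|---|
| s = 12 | 12 + 24 = hour 36 | none |
| s = 6 | 6 + 24 = hour 30 | none |
| s = 0 | 0 + 24 = hour 24 | none |
| s = −6 | −6 + 24 = hour 18 | just under 6 hours |
| s = −18 | −18 + 24 = hour 6 | just under 18 hours |

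**Reading the table**

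1. For s of 0 or more, the trigger always falls after the deadline. The report is late if the system is still down at hour 24, the site had not already reported electronically, and it waited for the trigger.
2. For s between −24 and 0, a report on time is possible. The margin runs from almost nothing to almost a full day.
3. If the system returns before hour 24, electronic entry can still meet the deadline, whatever the value of s.

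**Does another section close the gap?**

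- The other paper or telephone route in Section 12.5.6 applies only after the tool has been closed at the end of the study at that site.
- Section 7.4.1.6 asks for prompt notification of treatment-related SAEs but gives no procedure for an outage.
- The 24-hour notice to the Medical Monitor in Section 12.2 covers only subjects who meet the liver stopping criteria.
- Section 12.5.6 also points to a contacts page for SAE receipt. That page was not in the copy reviewed, so its contents cannot be checked.

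**The case against.** The strongest reply is that the two sections can both be obeyed. Section 12.5.6 makes paper compulsory after a long outage. It does not say that paper is allowed only then, and it calls the electronic tool the primary mechanism, not the sole one. The duty in Section 7.4.1.1 is unconditional and no outage suspends it. A careful site could fax early and comply with everything.

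That stands as a reading of the words. A reader might infer that the protocol orders sites to wait, or that any outage makes a report late. The text supports neither: earlier faxing is not forbidden, and outages that end before hour 24, or that began well before the site learned of the event, leave room for a timely report. What the reply does not remove is that the only stated trigger during the study is longer than the reporting window, so the written procedure gives no help in the case where it is most needed.

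A reader might also infer that the citation of Section 12.5.4 misdirects sites. It is imprecise, but the same section's NOTE already names Section 12.5.6, and Section 12.5.4 does cover the recording half of the sentence. That point is editorial.

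It is also fair to say that the documents give no frequency or duration of outages, so the number of late reports cannot be estimated, and that no endpoint or analysis is touched.

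**Conclusion.** The concern holds in this limited form: a site that follows Section 12.5.6 **can** report late. Lateness needs three things together: an outage that starts at or after the site learns of the event, a system still down at hour 24, and a site that waits for the stated trigger. An outage that started h hours earlier (h below 24) leaves just under h hours to fax.

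The conclusion rests on counting the 24 hours from the site learning of the event, which the protocol does not state, and on the available text, because the contacts page could not be seen. It is a gap in safety-reporting procedure worth correcting because the correction is nearly free. It is not evidence that late reports will be common, and it has no bearing on the dose-response analysis.

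**What to change.** - **Section 12.5.6:** tie the backup to the deadline instead of the length of the outage. Suggested wording: *If the electronic system is unavailable, the site will fax the paper SAE form so that it is received within 24 hours of learning of the event, and will enter the data electronically once the system is available.*
- **Section 7.4.1.1:** state that the 24 hours run from the site learning of the event.
- **Optional tidy-up:** point the cross-reference in the deadline sentence to Section 12.5.6.

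The cost is about one sentence in each section and an occasional extra fax during a short outage. The paper form and the hotline already exist. The wording should be checked against the contacts page so that the two agree.

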7.4.1.2. Adverse Events of Special Interest

The following have been identified as adverse events of special interest (AESIs) for GSK1278863 based on nonclinical studies, the mechanism of action and pharmacological activity of GSK1278863, current information about hypoxia-associated pathophysiology, studies of genetically engineered animal models, and naturally occurring mutations in man:

- Thrombosis and tissue ischemia secondary to excessive erythropoiesis
- Death, MI, stroke, venous thromboembolism, thrombosis of vascular access
- Cardiomyopathy
- Pulmonary artery hypertension
- Cancer-related mortality and tumor progression and recurrence
- Esophageal and gastric erosions
- Proliferative retinopathy, macular edema, choroidal neovascularization

• Exacerbation of rheumatoid arthritis

The results of any investigation should be recorded in the relevant sections of the subject's eCRF

7.4.1.3. Method of Detecting AEs and SAEs

Care will be taken not to introduce bias when detecting AEs and/or SAEs. Open-ended and non-leading verbal questioning of the subject is the preferred method to inquire about AE occurrence. Appropriate questions include:

- "How are you feeling?"
- "Have you had any (other) medical problems since your last visit/contact?"
- "Have you taken any new medicines, other than those provided in this study, since your last visit/contact?"

7.4.1.4. Follow-up of AEs and SAEs

After the initial AE/SAE report, the investigator is required to proactively follow each subject at subsequent visits/contacts. All SAEs and non-serious AEs of special interest (as defined in Section 7.4.1.2) will be followed until resolution, until the condition stabilizes, until the event is otherwise explained, or until the subject is lost to follow-up (as defined in Section 5.6.3). Further information on follow-up procedures is given in Section 12.5.4.

7.4.1.5. Cardiovascular and Death Events

For any events that may represent the cardiovascular events detailed in Section 12.5.3 and all deaths, whether or not they are considered SAEs, specific Cardiovascular (CV) and Death sections of the CRF will be required to be completed. These sections include questions regarding cardiovascular (including sudden cardiac death) and non-cardiovascular death.

The CV CRFs are presented as queries in response to reporting of certain CV MedDRA terms. The CV information should be recorded in the specific cardiovascular section of the CRF within one week of receipt of a CV Event data query prompting its completion.

The Death CRF is provided immediately after the occurrence or outcome of death is reported. Initial and follow-up reports regarding death must be completed within one week of when the death is reported.

7.4.1.6. Regulatory Reporting Requirements for SAEs

Prompt notification by the investigator to GSK/PPD (or designee) of SAEs related to study treatment (even for non- interventional post-marketing studies) is essential so that

legal obligations and ethical responsibilities towards the safety of subjects and the safety of a product under clinical investigation are met.

GSK has a legal responsibility to notify both the local regulatory authority and other regulatory agencies about the safety of a product under clinical investigation. GSK will comply with country specific regulatory requirements relating to safety reporting to the regulatory authority, Institutional Review Board (IRB)/Independent Ethics Committee (IEC) and investigators.

Investigator safety reports are prepared for suspected unexpected serious adverse reactions according to local regulatory requirements and GSK policy and are forwarded to investigators as necessary.

An investigator who receives an investigator safety report describing a SAE(s) or other specific safety information (e.g., summary or listing of SAEs) from GSK will file it with the IB and will notify the IRB/IEC, if appropriate according to local requirements.

7.4.2. Pregnancy

- Details will be collected about all pregnancies reported after the start of dosing and until the Follow-up Visit.
- If a pregnancy is reported then the investigator should inform GSK within 2 weeks of learning of the pregnancy and should follow the procedures outlined in Section 12.6.2.

Subjects must permanently discontinue study medication if pregnancy occurs (see Section 5.6.1).

7.4.3. Physical Exams

- A complete physical examination will include, at a minimum, assessment of the Cardiovascular, including vascular access, Respiratory, Gastrointestinal and Neurological systems. Height and weight will also be measured and recorded.
- Investigators should pay special attention to clinical signs related to previous serious illnesses.

7.4.4. Vital Signs

Vital signs include systolic blood pressure (SBP), diastolic blood pressure (DBP), heart rate (HR), height and weight. Three measurements of SBP, DBP and HR will be recorded at each study-specified visit. Measurements will be taken from the subject while in a seated position or semi-supine in the dialysis chair. Vital signs will be recorded pre-dialysis (except weight) and post-dialysis as outlined in Section 7.1. Height will be measured during the Screening period (at Day -14) only. Additional details are provided in the SRM.

204836

Full 12-lead ECGs will be recorded in subjects while in a supine position at the times as outlined in Section 7.1, Time and Events Table. The parameters to be measured include heart rate, PR interval, QRS duration, and QT (uncorrected) interval. QTcB is to be calculated.

While it is preferred that ECGs are performed pre-dialysis, it is acceptable for this to occur at any time during the dialysis session. However, it is requested that the timing of the ECGs be performed consistent with the Screening assessment.

At any study visit when ECGs are performed, two additional ECGs are required if initial ECG indicates prolonged QTcB using the manually-calculated QTcB value. The average QTcB value of three ECGs will be used to determine eligibility as provided in Section 5.3, Eligibility Criteria. Additional details are provided in the SRM.

7.4.6. Clinical Safety Laboratory Assessments

All protocol required laboratory assessments, as defined in Table 3, must be conducted in accordance with the Laboratory Manual, and Protocol Time and Events Schedule. Laboratory requisition forms must be completed and samples must be clearly labelled with the subject number, protocol number, site/center number, and visit date. Details for the preparation and shipment of samples will be provided by the laboratory and are detailed in the SRM. Reference ranges for all safety parameters will be provided to the site by the laboratory responsible for the assessments.

If additional non-protocol specified laboratory assessments are performed at the institution's local laboratory and result in a change in subject management or are considered clinically significant by the investigator (e.g., SAE or AE) the results must be recorded in the eCRF.

Refer to the SRM for appropriate processing and handling of samples to avoid duplicate and/or additional blood draws.

All study-required laboratory assessments will be performed by a central laboratory, apart from the HemoCue Hgb, with the results of each test entered into the eCRF.

NOTE: Local laboratory results are only required in the event that the central laboratory results are not available in time for either a treatment and/or response evaluation to be performed. If a local sample is required it is important that the sample for central analysis is obtained at the same time. Additionally, if the local laboratory results are used to make either a treatment or response evaluation, the results must be entered into the eCRF.

Hematology, clinical chemistry and additional parameters to be tested are listed in Table 3.

Table 3 Protocol Required Safety Laboratory Assessments

Laboratory Assessments	Parameters		
	Platelet Count	RBC Indices:	WBC Count with Differential:
	RBC Count	MCV	Neutrophils
Hematology	Hemoglobin	MCH	Lymphocytes
	Hematocrit	MCHC	Monocytes
	WBC Count (absolute)	RDW	Eosinophils
	Reticulocyte Count	CHr	Basophils
	Potassium	AST (SGOT)	Total and direct/indirect bilirubin
Clinical	Sodium	ALT (SGPT)	Total Protein
Chemistry	Glucose	Calcium (Albumin adjusted)	Alkaline Phosphatase
	Albumin	Phosphate	
	Erythropoietin	Vascular Endothelial Growth Factor	Hepcidin
Other laboratory	Serum ferritin	Serum iron	Serum transferrin
Tests	Transferrin saturation (% saturation) Vitamin B12	Unbound iron binding capacity	Folate
Other Screening Tests ¹	FSH	Estradiol	Serum hCG Pregnancy test

NOTE: Details of Liver Chemistry Stopping Criteria and Required Actions and Follow-Up Assessments after liver stopping or monitoring event are given in Section 12.2 Appendix 2 1 As required per Appendix 6

All laboratory tests with values that are considered clinically significantly abnormal during participation in the study or within 5 days after the last dose of study treatment should be repeated until the values return to normal or baseline. If such values do not return to normal within a period judged reasonable by the investigator, the etiology should be identified and the sponsor notified.

7.5. Pharmacokinetics/Pharmacodynamics

Blood samples for PK (GSK1278863 and metabolites) and PD (EPO, VEGF, hepcidin) will be collected from all subjects as outlined in Table 2.

7.5.1. Blood Sample Collection

Blood samples for pharmacokinetic (PK) analysis of parent GSK1278863 and metabolites (GSK2391220 [M2], GSK2531403 [M3], GSK2487818 [M4], GSK2506102 [M5], GSK2531398 [M6], and GSK2531401 [M13]) will be collected at the time points indicated in Section 7.1, Time and Events Table. The actual date and time of each blood sample collection will be recorded. The timing of PK samples may be altered and/or PK samples may be obtained at additional time points to ensure thorough PK monitoring.

For the PK/PD visits outlined in Table 2, sample times are approximate; however, it is imperative that **the actual date and time** of sampling is recorded in the eCRF.

- At the Day 1 Visit, pre-dose PK/PD samples will be obtained from all subjects. Record the date and time of the last ESA dose administered prior to PD sampling and the date and time of the GSK1278863 dose administered at this visit.
- At Day 15 Visit, post-dose PK/PD samples will be obtained. Initial PK/PD samples will be obtained from all subjects soon after arrival.
 - Record the date and time of the last two GSK1278863 doses taken prior to the Day 15 Visit (the last dose of GSK1278863 may be taken early on the day of the Day 15 Visit, or in the evening of the day before).
 - At Day 29 Visit, pre- and post-dose PK/PD samples will be obtained. Record the
 date and time of the last GSK1278863 dose taken prior to the Day 29 Visit, and
 the date and time of the dose taken at the Day 29 Visit.

Based on the time of dosing, samples may be obtained before, during, and after the hemodialysis procedure. The start date/time and stop date/time of the hemodialysis procedure at the Day 15 and 29 Visits will be recorded.

Details of PK blood sample collection (including volume to be collected), processing, storage and shipping procedures are provided in the Study Reference Manual (SRM).

7.5.2. Sample Analysis

Plasma PK analysis will be performed under the management of Bioanalytical Science and Toxicokinetics, PTS DMPK, GlaxoSmithKline, the details of which will be included in the SRM. Concentrations of parent GSK1278863 and metabolites (GSK2391220 [M2], GSK2531403 [M3], GSK2487818 [M4], GSK2506102 [M5], GSK2531398 [M6], and GSK2531401 [M13]) will be determined in plasma samples using the currently approved bioanalytical methodology. Raw data will be archived at the bioanalytical site (detailed in the SRM).

Analysis of plasma EPO, VEGF and hepcidin are described in the SRM.

